4.1 OVERALL DESIGN

In aim 1, with relevant stakeholders in adolescent HIV, we will collaboratively develop the DiSC intervention, then adapt and pilot test the intervention.

In aim 2, we will conduct a cluster randomized trial (cRCT) in up to 24 sites in western Kenya (12 randomized to intervention and 12 to control) (Figure 1).

Figure 1: Study design, main activities, and outcomes

Adapted from NIH Behavioral and Social Intervention Clinical Trial Protocol Template v3.0 - 20180827

Study hypothesis

- Primary and secondary outcomes: We hypothesize that the DiSC intervention will result in better retention, adherence and viral suppression among adolescents in the intervention sites compare to those in control sites. Hypothesized psychosocial outcomes will include better psychosocial and family support, mental health, family support and adolescent self-efficacy.
- We hypothesize the DiSC intervention will be associated with improved clinic efficiency (client wait time), and will be cost effective.
- The DiSC Intervention will be feasible, acceptable to HCW and adolescents but will require clinic specific intervention adaptations.

Randomization

Up to 24 clinics will be randomized in a 1:1 ratio using computer generated random numbers to either intervention or control, using restricted randomization to balance by county, aiming to balance the numbers of clinics from each county between arms. Timing of randomization will be prior to study start. Randomization will be done at the University of Washington by a biostatistician not involved in study procedures. A list of clinics with their allocation arms will be sent to the study team. We will perform individual substitutions of sites on a case by case basis, as needed (e.g. if the site no longer meets an eligibility criterion). The intervention is administered at the clinic-level; it is not possible to blind participating clinics or study team members.

Study intervention

The DiSC intervention is comprised of a system to assign adolescents to care based on their health needs and the different levels of care for each assignment group. Control sites will continue with standard of care approaches for adolescent clinic visits (usually 1-3 monthly visits) regardless of health care needs and additional support as needed.

Analysis

Adapted from NIH Behavioral and Social Intervention Clinical Trial Protocol Template v3.0 - 20180827

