9.2 SAMPLE SIZE DETERMINATION

Sample Size and Power for primary outcome

In our sample of HIV care facilities with >1,000 clients enrolled overall, we anticipate at least 10% will be eligible adolescents and young adults or about 100-200 AYA per clinic on average. Based on our UG3 data, we assume that 75% will be in care (not LTFU) and viral suppression of 64% (85% suppressed x 75% actively in care). Given a minimum of 20 facilities in the trial (minimum 10 per arm), we estimated the minimum average number of AYA per facility to detect a 15-20% change in retention using EMR data. We assumed 80% power, an $\alpha=0.05$ and coefficient of

Adapted from NIH Behavioral and Social Intervention Clinical Trial Protocol Template v3.0 - 20180827

variation of 0.15. In table 3a below, we can detect a 17% percentage point different (75% to 93%) with an average of 100 AYA per facility and 20 facilities. The same estimates hold for as few as 50 AYA per arm and up to 170 per arm. Detecting less than a 17% percentage point difference would require more facilities per arm or at least 180 AYA per facility.

Secondary outcomes and assumptions:

Viral suppression: An average of 50 AYA VL records per facility and a minimum of 10 facilities per arm would be sufficient to detect a change from 64% to 81%, assuming 80% power, an $\alpha=0.05$ and coefficient of variation of 0.15.

Cohort analyses: Based on UG3 enrollment data in the AYA cohort, we assume that about 50% of the total AYA clinic population to enroll in the cohort and set 50 as the average enrollment target per facility. Separate power and sample size calculations will be performed based on the specific exposure and outcome. When the intervention is the exposure, we will assume to have adequate power to detect at least a 17% percentage point difference in proximate outcomes (e.g. implementation and client outcomes)

Table 3a: Minimum Sample of AYA per Facility for the Primary ITT Analysis of Retention

	Retention % in the intervention arm	n=100 AYA per facility	Facilities per arm	n=50 AYA per facility	Facilities per arm
75%	90%	100	13	50	14
75%	92%	100	11	50	12
75%	93%	100	10	50	10

Table 3b: Summary of sample size estimates by outcome

Outcome	Source	Sample size	
		Intervention	Control
Retention	EMR data	3000	3000
Unsuppressed VL	EMR data	3000	3000
Mediators and secondary outcomes	Adolescent surveys	1500	1500
	Caregiver surveys	450	450
Implementation outcomes	HCW surveys	120	120
	HCW implementation logs	12	0

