2.2. Sample size considerations

2.2.1. Sample size and power for primary outcome

In our sample of HIV care facilities with >1,000 clients enrolled overall, we anticipate at least 10% will be eligible adolescents and young adults (AYA), with about 100-200 AYA per clinic on average. Based on our UG3 data, we assume that 75% will be in care (not LTFU) by the end of 12-month follow-up period. Given a minimum of 24 facilities in the trial (minimum 12 per arm), we estimated the minimum average number of AYA per facility to detect a 14-18% point change in retention using EMR data. Assuming 12 facilities per arm, 80% power, $\alpha=0.05$ and coefficient of variation of 0.10 (Table 2), we can detect a 14%-point difference (75% to 89%) with at least 150 AYA per facility, and a 15%-point difference (75% to 90%) with at least 50 AYA per facility. Assuming coefficient of variation of 0.15, we can detect a 17%-point difference (75% to 92%) with at least 50 AYA per facility (Table 2). Detecting a less than 14%-point difference or if assuming a larger correlation coefficient of individuals within a facility would require more participants per facility or more facilities per arm.

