2.2.2. Secondary outcomes and assumptions

Viral suppression: An average of 50 AYA VL records per facility and a minimum of 12 facilities per arm would be sufficient to detect a change from 64% to 82%, assuming 80% power, an $\alpha=0.05$ and coefficient of variation of 0.10 (Table 2).

Table 1. Sample size calculation of number of facilities per arm for the ITT analysis of retention and viral suppression

AYA per facility	ICC	Estimated proportion in study arm									
		Control	Intervention								
		75%	85%	86%	87%	88%	89%	90%	91%	92%	93%
200	0.10		26	21	18	15	12	11	9	8	7
150			27	22	18	15	12	11	9	8	7
100			27	22	18	15	13	11	9	8	7
50			30	24	20	17	14	12	10	9	8
	0.15	75%	85%	86%	87%	88%	89%	90%	91%	92%	93%
200			39	31	26	21	18	15	13	11	10
150			39	32	26	22	18	16	13	12	10
100			40	32	26	22	19	16	14	12	10
50			42	34	28	23	20	17	14	12	11
		64%	80%	81%	82%	83%	84%	85%	86%	87%	88%
200	0.10		13	11	10	9	8	7	6	6	5
150			13	12	10	9	8	7	7	6	5
100			13	12	10	9	8	7	7	6	5
50			15	13	11	10	9	8	7	7	6
	0.15	64%	80%	81%	82%	83%	84%	85%	86%	87%	88%
200			19	17	15	13	12	10	9	8	8
150			19	17	15	13	12	10	9	8	8
100			19	17	15	13	12	11	10	9	8
50			20	18	16	14	12	11	10	9	8

ICC: intraclass correlation coefficient; sample size estimated by assuming study power of 80%, significance level of 0.05 and coefficient of variation of 0.10

Section 3. Study Data Analysis

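### The three retention power claims in SAP 2.2.1 make no allowance for having only 24 clinics: at 12 per arm, power is about 76% to 78% rather than 80%

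*SAP*

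**What the plan says.** SAP 2.2.1 makes three retention claims, each for 12 clinics per arm, 80% power and alpha 0.05:

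- With a clustering value of 0.10, "we can detect a 14%-point difference (75% to 89%) with at least 150 AYA per facility".
- With the same value and at least 50 adolescents and young adults (AYA) per clinic, 75% to 90%.
- With a clustering value of 0.15 and at least 50 AYA per clinic, 75% to 92%.

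SAP 2.2.2 adds a viral-suppression claim of 64% to 82%, with 50 records per clinic, 12 clinics per arm and 0.10.

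The prose calls 0.10 and 0.15 coefficients of variation. The facilities-per-arm table in 2.2.2 heads the same values ICC, and its footnote uses both terms: "ICC: intraclass correlation coefficient; sample size estimated by assuming study power of 80%, significance level of 0.05 and coefficient of variation of 0.10".

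On the number of clinics, the SAP writes "Given a minimum of 24 facilities in the trial (minimum 12 per arm". Protocol 9.2 writes "Given a minimum of 20 facilities in the trial (minimum 10 per arm", and protocol 4.1 writes "Up to 24 clinics will be randomized in a 1:1 ratio".

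**The concern.** Clinics are randomised, so the precision of the arm comparison depends on between-clinic variation estimated from 24 units. A test that holds its 5% level refers the statistic to a t distribution with 22 degrees of freedom, or uses an equivalent correction. Power computed with 1.96 and 0.84 then comes out slightly too high. Neither the SAP's sample-size text nor its primary model in 3.4 (a Poisson mixed model with robust standard errors) mentions such a correction.

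Readers will use 2.2.1 to judge a null or borderline result. For the headline effect, the SAP implies a 20% chance of missing a true difference, while the t-based figure is 24%. The two documents also disagree on whether 24 clinics is the fewest or the most, and power falls with each clinic lost.

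**Working it through.** **Inputs.** Control retention is 75%. Intervention rates, AYA per clinic (m) and clustering values (ρ) are those in SAP 2.2.1 and 2.2.2. There are c = 12 clinics per arm. Alpha is 0.05; its sidedness is not stated, and two-sided reproduces the table. ρ is read as an ICC.

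**Reproducing the SAP table.** Clinics per arm:

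n = (1.960 + 0.842)² × [p₁(1−p₁) + p₂(1−p₂)] × [1 + (m−1)ρ] / [m (p₂−p₁)²], rounded up.

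Headline cell: the variance sum is 0.1875 + 0.0979 = 0.2854. The design effect is 1 + 149 × 0.10 = 15.9, and 15.9/150 = 0.106. So n = 7.849 × 0.2854 × 0.106 / 0.0196 = 12.11, printed as 12.

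This formula matches 141 of 144 cells. The three exceptions all print lower than rounding up would give: 12.11 as 12, 9.003 as 9 and 13.05 as 13. Pooled-variance, arcsine and true-coefficient-of-variation formulas match fewer cells. The method is therefore normal quantiles with an ICC design effect. Of the claims made in prose, only the headline is rounded down. The others compute to 11.42, 11.84 and 10.81.

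**Power with 22 degrees of freedom.** The variance is unchanged. The noncentrality is δ = (p₂−p₁) / √{variance sum × [1 + (m−1)ρ] / (m c)}. Power is taken from the noncentral t with 2c−2 = 22 df and critical value 2.074.

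Headline: δ = 0.14 / √(0.2854 × 0.106 / 12) = 2.788.

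| Claim | m | ρ | δ | Power, normal | Power, t(22) |
|---|---|---|---|---|---|
| 75% vs 89% | 150 | 0.10 | 2.788 | 79.6% | 76.0% |
| 75% vs 90% | 50 | 0.10 | 2.872 | 81.9% | 78.4% |
| 75% vs 92% | 50 | 0.15 | 2.820 | 80.5% | 76.9% |
| 64% vs 82% (viral suppression) | 50 | 0.10 | 2.952 | 84.0% | 80.6% |

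The rounding slip accounts for 80.0 − 79.6 = 0.4 point. The rest of the headline shortfall, 79.6 − 76.0 = 3.6 points, is normal versus t.

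**Detectable differences at 80% power, 12 per arm, t(22).** The intervention rates are 89.6%, 90.3% and 92.5%, so the differences are 14.6, 15.3 and 17.5 points. The smallest whole-point differences that reach 80% are 15 (82.5% power), 16 (84.4%) and 18 (82.7%).

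**Simulation check.** Beta-binomial clinics with ICC 0.10, 150 AYA each and 12 per arm, analysed by a clinic-level t-test, gave 76.6% power for the headline effect with type I error 4.9%. Using 1.96 as the cut-off gave 79.9% power, but type I error rose to 6.1%. So in this simulation roughly 80% is reached only by a test that exceeds its nominal level.

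**Scenario at the protocol's minimum of 10 per arm.** With 18 df, power for the SAP's three retention effects is 67.3%, 69.8% and 68.3%. By the normal method it is 72.1%, 74.6% and 73.1%.

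**The case against.** The strongest reply is that the shortfall is small: 0.3 to 0.6 point in the detectable difference, which is less than the uncertainty in an assumed 75% control rate or in an ICC that the SAP itself varies from 0.10 to 0.15. That stands, and it limits the weight of the point. It does not make the stated 80% correct.

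The label matters more than the quantiles. If 0.10 were truly a between-clinic coefficient of variation, as the prose says, 12 clinics per arm would give about 96% power for the headline effect by t. But the table does not reproduce on that reading, and its own column says ICC. The figures here therefore depend on the ICC reading, and the SAP needs to settle the term.

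The calculation, like the SAP's, uses one binary outcome per participant, whereas the primary analysis in 3.4 is of visit-level missed visits. So 76% is the power of a clinic-level comparison under the SAP's own assumptions, not of the planned model. That limit also stands.

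A reader might infer three stronger things that the documents do not support:

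- That every power claim in the SAP fails. The viral-suppression claim meets its 80%.
- That rounding down drives the shortfall. It costs 0.4 point.
- That the trial has 67% power. That figure puts the SAP's 14-point effect on the protocol's 20-clinic minimum. The protocol tied 20 clinics to 75% vs 93% and never claimed 80% power for 14 points there. SAP 1.2 and protocol 4.1 both describe 12 clinics in each arm.

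**Conclusion.** The point holds as a modest correction. Each of the three retention claims in SAP 2.2.1 falls short of 80% once 24 clinics are allowed for: about 76%, 78% and 77%. The differences detectable at 80% are about 14.6, 15.3 and 17.5 points. The design is not undermined, and no clinic number has to change.

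The result assumes that 0.10 and 0.15 are ICCs, that alpha is two-sided, that clinics are of equal size, that each participant contributes one binary outcome, and that the test holds its size on 22 df.

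Separately, the documents do conflict on the number of clinics: 24 is a minimum in the SAP and a maximum in the protocol, whose minimum is 20. The 67%, 70% and 68% at 20 clinics show what that conflict could cost, and only as a conditional scenario.

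**What to change.** In SAP 2.2.1, restate the three retention claims at 12 clinics per arm. In whole points they become 15 (150 AYA, ICC 0.10), 16 (50 AYA, ICC 0.10) and 18 (50 AYA, ICC 0.15). Alternatively, keep the present effects and state their power as 76%, 78% and 77%. Recompute the facilities-per-arm table with t quantiles and round every cell up. The viral-suppression claim can stay.

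Use ICC for 0.10 and 0.15 in both the prose and the footnote, and correct the footnote so that it covers the 0.15 blocks as well.

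Reconcile the SAP's minimum of 24 facilities with the protocol's maximum of 24 and minimum of 20. If 20 remains possible, report power there as a labelled scenario: about 67%, 70% and 68% for the SAP's three effects.

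The cost is a text and table revision, with no extra clinics or participants.

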2.2.2. Secondary outcomes and assumptions

Viral suppression: An average of 50 AYA VL records per facility and a minimum of 12 facilities per arm would be sufficient to detect a change from 64% to 82%, assuming 80% power, an $\alpha=0.05$ and coefficient of variation of 0.10 (Table 2).

Table 1. Sample size calculation of number of facilities per arm for the ITT analysis of retention and viral suppression

AYA per facility	ICC	Estimated proportion in study arm									
		Control	Intervention								
		75%	85%	86%	87%	88%	89%	90%	91%	92%	93%
200	0.10		26	21	18	15	12	11	9	8	7
150			27	22	18	15	12	11	9	8	7
100			27	22	18	15	13	11	9	8	7
50			30	24	20	17	14	12	10	9	8
	0.15	75%	85%	86%	87%	88%	89%	90%	91%	92%	93%
200			39	31	26	21	18	15	13	11	10
150			39	32	26	22	18	16	13	12	10
100			40	32	26	22	19	16	14	12	10
50			42	34	28	23	20	17	14	12	11
		64%	80%	81%	82%	83%	84%	85%	86%	87%	88%
200	0.10		13	11	10	9	8	7	6	6	5
150			13	12	10	9	8	7	7	6	5
100			13	12	10	9	8	7	7	6	5
50			15	13	11	10	9	8	7	7	6
	0.15	64%	80%	81%	82%	83%	84%	85%	86%	87%	88%
200			19	17	15	13	12	10	9	8	8
150			19	17	15	13	12	10	9	8	8
100			19	17	15	13	12	11	10	9	8
50			20	18	16	14	12	11	10	9	8

ICC: intraclass correlation coefficient; sample size estimated by assuming study power of 80%, significance level of 0.05 and coefficient of variation of 0.10

Section 3. Study Data Analysis

3.1. Study accrual

Per CONSORT guidelines, we will report the number of facilities who:

- Underwent screening
- Met inclusion criteria
- Did not meet inclusion criteria (and reasons)
- Enrolled in the study and were randomized
- # of people at facility that were treated as per study protocol

3.2. Trial profile

A CONSORT diagram will show the number of clinics and ALHIV clients per clinic (cluster) randomized to each arm (see Figure 1). We will report the number of clinics selected for inclusion, assignment to intervention or control, and the number of HCWs enrolled per site. Clinic-specific information, including ALHIV client volume, number of HCWs, and any pre-trial adolescent-specific services will be reported.

3.4. Analysis of retention

Retention will be evaluated using an indicator of missed visits. A missed visit will be defined as a participant not seen within 30 days of a scheduled visit during follow-up since the first stepped care visit to 12 months. Each scheduled visit will be classified as missed versus not missed and analysis will use repeated measures per participant. The proportion of missed visits will be compared between study arms using mixed-effects Poisson regression with random effects for facility and participant and robust standard errors.

Sub-group analyses for retention will be performed by gender and age-group. Facility factors, including concurrent adolescent-friendly services and high/low performance will be evaluated as modifiers of intervention effectiveness.

Table 4. Analysis of missed visits

	Overall	Control	Intervention	Intervention vs. control
Missed visits per participant				^a RR (95% CI)
Median (IQR)				
Number of scheduled visits				
Number of missed visits (%)				
Missed visits over all participants				
Count (proportion)				
Number of scheduled visits				
Number of missed visits (%)				
Number of AYA ever missed a visit (%)				

^a Estimated by mixed-effects Poisson regression with random effects for facility and participant and robust standard errors

*Excluding TCA that had miss/no-miss status censored or missing

*Models adjusted for any factors differing between arm with statistical significance at enrollment

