6.1.2 ADMINISTRATION AND/OR DOSING

The study team will conduct training for HCWs at intervention and control sites. At intervention sites, the training will focus on intervention use and data collection while in control sites, training will focus on data collection. At baseline, the study teams will assist HCWs to identify score categories for each step of care. The clinical tool will be uploaded onto handheld tablets or on paper tools, according to HCW preferences and will be used at ALHIV scheduled visits.

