1.2. DiSC Cluster RCT Objectives

Primary: To compare retention during 12-month follow-up among ALHIV in 12 HIV clinics receiving DiSC intervention to retention among ALHIV in 12 similar control clinics receiving standard of care. Participating clinics will be high-volume HIV clinics in Homabay, Kisumu and Migori counties, all in Western Kenya.

Secondary: To evaluate the effect of the DiSC intervention on HIV cascade outcomes (viral non-suppression, receiving differentiated care, adherence).

Section 2. Study outcomes

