2.1. Summary of primary and secondary outcomes

Table 1. Outcome definitions and assessment

Outcome	Indicator	Source	Timing
Primary outcome			
Retention in care	Missed visits: Not seen within 30 days of a scheduled visit.	EMR data (Visit Date, TCA)	All visits occurring during the 12-month period after the study enrollment visit*
Secondary outcomes			
Loss to follow-up	Not return to care within the 12 months study interval	EMR data (Visit Date, TCA)	All visits after the first study visit until event or end of follow-up at 12 months. Participants marked as 'transferred out' or 'died' will be censored.
Viral non-suppression	Having HIV viral load (VL) >1,000 copies/mL	NASCOP data, abstraction of paper records	All visits from enrollment to 12 months follow-up*
Receiving differentiated care	
 Long inter-visit interval Fast-track visit 	EMR data (TCA, Care Model)	All visits from enrollment to 12 months follow-up*
Adherence	Pill coverage estimated by days of dosing and inter-visit interval since last visit >80%	EMR data (Visit Date, next Visit Date, Duration)	All visits from enrollment to 12 months follow-up*

*time window up to 12 months + 30 days

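### SAP 3.4 starts the primary-outcome window at a stepped care visit, which control clinics do not have; SAP Table 1 starts it at enrolment

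*SAP*

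**What the plan says.** SAP 3.4 defines a missed visit as one where the participant is not seen within 30 days of a scheduled visit, and counts such visits "during follow-up since the first stepped care visit to 12 months".

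SAP Table 1 (section 2.1) sets the timing of the same primary outcome as "All visits occurring during the 12-month period after the study enrollment visit", with a footnote giving a "time window up to 12 months + 30 days". Its loss-to-follow-up row uses other words for the start: "All visits after the first study visit until event or end of follow-up at 12 months". The rows for viral non-suppression, differentiated care and adherence all start at enrolment. The footnote to SAP Table 4 also looks to enrolment: "Models adjusted for any factors differing between arm with statistical significance at enrollment".

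On what each arm receives, SAP 1.2 compares the DiSC clinics with "12 similar control clinics receiving standard of care", and Protocol 4.1 says "Control sites will continue with standard of care approaches for adolescent clinic visits". Protocol 6.1.2 says that the clinical tool "will be used at ALHIV scheduled visits", and that training in control sites concentrates on data collection. Protocol 9.3 commits to an intent-to-treat analysis of effectiveness.

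**The concern.** The primary outcome has two stated start points. The one in the section that specifies the analysis is an event of the intervention itself. An analyst who follows 3.4 literally has a start date for DiSC participants and none for controls, and would have to supply one. Protocol 4.1 says that study team members cannot be blinded, so the choice should be settled in the text and not left until data are in hand.

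What is at stake is comparability of the arms. A start point that depends on receiving the intervention, used in one arm only, would decide which visits and which people are counted in that arm by something that happens after randomisation. It would also be tied to the outcome: a first stepped care visit has to be attended, and attendance is what is being measured.

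**Working it through.** The plan states no figure on this point, so there is none to reproduce. The check is a comparison of texts.

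**Step 1: start points.**

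| Place | Outcome | Start of window |
|---|---|---|
| SAP 3.4 | Missed visits (primary) | First stepped care visit |
| SAP Table 1, primary row | Missed visits (primary) | Study enrolment visit |
| SAP Table 1, loss to follow-up | Secondary | First study visit |
| SAP Table 1, viral load, differentiated care, adherence | Secondary | Enrolment |

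No section defines the first stepped care visit or says that it is the enrolment visit.

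**Step 2: does the 3.4 start point exist in both arms?** Protocol 6.1.1 describes stepped care as the DiSC intervention: health workers assign adolescents to steps. SAP 1.2 and Protocol 4.1 give control clinics standard of care, and Protocol 6.1.2 does not train them in the intervention. No section names a control-arm counterpart. The answer is no.

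**Step 3: must the two visits coincide in DiSC clinics?** They may. Protocol 5.5 recruits adolescents whom clinic staff refer, Protocol 10.1.1.1 requires written consent before the intervention starts, and Protocol 6.1.2 has the tool used at scheduled visits, so both could fall on one day. They need not. The implementation logs in Protocol 8.1 count adolescents attending separately from adolescents exposed to the intervention, Protocol 6.2.1 allows an initial implementation period of about 3 to 6 months, and Protocol 10.1.1.1 lists separate consent forms for the intervention and the surveys.

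**Step 4: what follows under each rule.**
- *Enrolment in both arms (Table 1).* Every scheduled visit after enrolment counts in the same way. The wording of 3.4 then has no effect.
- *3.4 taken literally.* The control arm has no start date, and the analysis cannot be run.
- *3.4 in DiSC clinics, enrolment in control clinics.* Take two participants who each miss the first appointment after enrolment and attend the next. The control participant's missed visit counts. If the tool was first used for the DiSC participant at that next visit, the DiSC participant's missed visit falls before the window and is lost. A DiSC participant who never has a stepped care visit contributes nothing, while a control participant with the same history contributes every missed visit.

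**Step 5: end of window.** Appointments due up to month 12, each watched for 30 days, need data to 12 months + 30 days. That is exactly the Table 1 footnote, so the two end points can be reconciled. The replacement text must keep them apart, though. If appointments due as late as 12 months + 30 days were eligible, classifying the last of them would need data to 12 months + 30 + 30 days, that is, 12 months + 60 days.

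**The case against.** The strongest reply is that this is one stray phrase. Table 1 is the SAP's table of outcome definitions and applies to both arms, the remaining secondary rows and the Table 4 footnote point to enrolment, and the protocol already commits to intent-to-treat. A sensible analyst would use enrolment throughout. In DiSC clinics the first stepped care visit may simply be the enrolment visit, since both need attendance.

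Most of that stands. A drafting slip is the likeliest explanation, and if enrolment is used in both arms there is no effect. It does not remove the point. Section 3.4 specifies the primary analysis, nothing says that Table 1 prevails over it, and the label means nothing in control clinics even if the two visits coincide elsewhere.

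A reader might also infer that the SAP contradicts itself on the end of the window, with 12 months in one place and 12 months + 30 days in the other. The documents do not support that. A missed visit is defined by a 30-day allowance, so both statements fit appointments due within 12 months and observed for 30 days each.

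**Conclusion.** The inconsistency is established from the text. The primary outcome has two start points, and the one in SAP 3.4 cannot be applied in control clinics.

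A reader might go further and infer that the primary comparison will be biased towards DiSC, or that the sponsor plans an analysis that is not intent-to-treat. The documents support neither. Bias arises only under a mixed rule that the SAP nowhere states. Even then, 'could favour DiSC' is as far as one can go, because visits attended before the tool was first used would be lost along with those missed.

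The size cannot be derived. It depends on how long after enrolment the first stepped care visit falls, how many DiSC participants never have one, and what proportion of visits is missed. The documents give none of these. The 75% in care at 12 months in SAP 2.2.1 describes people, not visits, and cannot stand in for the last. Any relative risk would rest on assumed inputs, so none is offered here. With Table 1's start point in both arms, the effect is nil.

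**What to change.** 1. In SAP 3.4, replace "during follow-up since the first stepped care visit to 12 months" with: *during follow-up, for visits scheduled from the study enrollment visit (defined identically in both arms) to 12 months, each observed for 30 days after its scheduled date (data to 12 months + 30 days)*. The definition of that visit should be written once and referred to elsewhere.
2. In the loss-to-follow-up row of SAP Table 1, use the same start point in place of the first study visit.
3. Add to SAP 3.4: *Participants are analysed by their clinic's randomised arm whether or not they had a stepped care visit.*

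The cost is two phrases, one sentence and the definition of the enrolment visit, with minor programming and no new data. Protocol section 9 has the SAP completed before database lock, and the change can be made within that limit.
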